3.1 Duration of Study Participation

The study will take place over a period of 2 years. Therefore for 18 months, data will be collected and analyzed from the clinicians' clinical practice on a quarterly basis.

3.2 Total Number of Subjects and Sites

A total of 52 clinicians will be recruited to participate in the study from PPMC

3.3 Inclusion Criteria

Clinic clinician participants must meet the following criteria for enrollment:

- 1) Provides care for inpatients with a cancer diagnosis at PPMC as a hospitalist or attending in the Department of Medicine,
- 2) Prescribing authority in Pennsylvania (i.e. physician, nurse practitioner, physician assistant),
- 4) Has cared for at least one patient with tobacco use disorder in the 30 days prior to recruitment,
- 5) English speaking

3.4 Exclusion Criteria

Exclusions include:

- 1) Unwillingness to prescribe varenicline, or
- 2) Unwillingness to assign varenicline management to TUT Service providers.

There will be no exclusion based on gender or race/ethnicity, consistent with our demonstrated ability to recruit representative samples in terms of demographic characteristics.

3.5 Subject Recruitment

ACC provides the highest quality medical care across the cancer care continuum to ~10,000 patients/year, reducing the cancer burden within an ethnically diverse catchment area consisting of 15 counties within the Greater Delaware Valley. We have extensive experience implementing tobacco research within clinics and working with clinicians on smoking cessation research ([name] et al., 2003; [name] et al., 2010). In a past study, we were able to recruit >200 primary care clinicians for training in treating nicotine dependence over 9 months ([name] et al., 2015), and in 14 months of recruitment in our ongoing organizational intervention trial (R01 CA202699), we have recruited 8 clinics, 295 patients and 120 clinicians. Further, [name], my close collaborator, has evaluated Clinical Decision Support Tools for promoting the treatment of tobacco dependence in Penn primary care.

Study leadership will first engage the ACC and its clinicians about the study. [name] is the Associate Director for Population Science at the ACC and regular (weekly) interactions with [name], Chief of the Cancer Service Line. [name], along with Drs. [name] and [name] (Radiation and Medical Oncology chairs) and Drs. [name] and [name] (and [name]), developed the Tobacco Use Treatment Service together. The proposed study, which simply adds a new default for an FDA-approved treatment for smoking, builds off of this collaboration. If the grant is supported, this team will work together to implement the proposed study.

Recruitment of clinicians will proceed via service-line leadership. Leaders of the Department of Medicine's hospital-based service lines (Teaching Medicine and Hospitalist services) will be briefed on the purpose and procedures for the study. Upon agreeing, a detailed email will be sent to individual admitting clinicians within each service line in order to inform them of the intent to alter the alert. The email will conclude with contact information for study personnel, in order to report questions, concerns or problems with the proposed workflow. Recruitment to participation is passive, absent notification to the contrary.

The same clinician sample will be contacted via email to participate in the survey supporting Specific Aim 3. This recruitment email will detail the goals of the survey, outline potential compensation, provide ways for clinicians to contact the study team with questions, and will note the voluntary and confidential nature of the study.

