5.6 Administration of Surveys and/or Process

Clinicians will be invited to complete a survey in the fall of 2023. We anticipate that this survey will take no more than 10 minutes to complete. The survey will measure clinician characteristics, opinions and experiences using the best practice alerts from the study, and related cognitive biases. We will keep the number of items as low as possible to reduce clinician fatigue and increase response rates. Please see the attached survey form for more detail.

Survey data will be collected through REDCap (a secure, web-based application for collecting and managing survey data that can be completed via computer or mobile device). Clinicians from the initial pilot (Aims 1-2) will be sent a link to the REDCap form via email. If a clinician clicks the link to learn more about participating, they will be routed to a webpage within REDCap that outlines all required consent elements. If they decide to participate, they will click a button which will route them to the first page of the survey. Clicking this button indicates their agreement to participate in this aim of the study. See the **Informed Consent** section for more details regarding this process.

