5.7 Subject Withdrawal

Participants may choose to withdraw from the study at any time. They do this by providing verbal or written communication to this effect. Withdrawal from the study will not impact employment status within the cancer center. The Principal Investigator may withdraw subjects who violate the study plan, to protect the subject for reasons related to safety or for administrative reasons. Whether or not each subject completes the study will be tracked.

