9.4 Risk Benefit Assessment

Evolving National Cancer Institute priorities have made rapid adoption of evidence-based TUT an essential component of comprehensive care. To date, little is known of the relative impact of BE strategies to systematically influence clinician decision-making about tobacco. The proposed study will test the notion that a simple, practical, electronic CDS intervention can significantly influence the clinical behaviors of both clinician and patient. As a result of this project, novel approaches to influencing clinical behaviors will be identified, forming the basis of a subsequent large-scale clinical trial assessing effectiveness under real-world conditions. This study is significant because the VM model for promoting clinician behavior change may also be applicable to other, non-cancer disorders, such as opioid dependence. If effective, the VM intervention would represent an inexpensive, straightforward way to reduce cancer morbidity and

mortality, and reduce the cost of cancer care incurred by both patients and the Commonwealth. The potential benefits of this study outweigh the potential risks.

10 Informed Consent

10.1 *Consent Process*

Aims 1 and 2. Since this is a pragmatic trial focused on improving implementation of higher-value evidence-based practices with minimal risk to patients, we are requesting a waiver of informed consent from clinicians and patients. We have received this in the past for these types of trials. We will identify clinicians at the practice sites and their patients using the EMR.

Aim 3. Participants will provide informed consent before completing survey measures. Because surveys will be completed remotely via REDCap, e-consent will be obtained as we have done previously (IRB 844846). When potential participants click the link to participate, they will be directed to a page within REDCap that outlines the required elements of informed consent. If they agree to participate, participants will indicate consent by clicking the “next” button which will take them to the electronic survey. If they do not want to participate, they will simply close the window.

All potential participants will be informed that participation is voluntary and they will be provided with the information that they need to make an informed choice. We will provide contact information to all potential survey respondents in case they have any questions before, during, or after completing the survey.

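### Does sending the Aim 3 barrier survey only to pilot clinicians, and so not to those excluded as unwilling to use varenicline, call for a change to the plan?

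*Combined protocol and SAP*

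**What the plan says.** Section 3.4 lists two exclusions: "Unwillingness to prescribe varenicline" and "Unwillingness to assign varenicline management to TUT Service providers". Section 3.5 has the clinicians in the Department of Medicine service lines emailed about the altered alert and given a study contact for questions or objections. It adds: "Recruitment to participation is passive, absent notification to the contrary". Section 10.1, under a requested consent waiver, says: "We will identify clinicians at the practice sites and their patients using the EMR".

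On the survey, section 3.5 states: "The same clinician sample will be contacted via email to participate in the survey supporting Specific Aim 3". Section 5.6 is more specific: "Clinicians from the initial pilot (Aims 1-2) will be sent a link to the REDCap form via email". It gives the content as follows: "The survey will measure clinician characteristics, opinions and experiences using the best practice alerts from the study, and related cognitive biases". Section 4.1 places the survey after the pilot, and the synopsis gives the Aim 3 analysis as mean ratings of barriers and facilitators.

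Two tracking steps are described. Section 5.7 says: "Whether or not each subject completes the study will be tracked". Section 7.2 adds protocol monitoring, which includes breaches of the eligibility criteria, for accrued cases.

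**The concern.** VM needs two things from a clinician: willingness to prescribe varenicline and willingness to pass its management to the TUT Service. Section 3.4 removes clinicians who lack either one. A survey of barriers to VM that goes only to those who remain seems to screen out the people with the plainest barrier.

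Section 2.1 wants the Aim 3 results to inform dissemination and itself notes that many clinicians switch the referral order off. A wider roll-out would meet objectors, and their reasons would be missing from the results or thinly represented. With no record of how many were excluded or opted out, a reader could not judge how selected the respondents were. The method of establishing unwillingness is also unstated, so it is unclear whether objectors leave the sample or stay in it silently.

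**Working it through.** The plan gives no figure for this point, so there is none to reproduce. The check sets the sections side by side and then asks what can be said about size.

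**Who is surveyed.** Section 3.5 alone is ambiguous, because the words about the same sample follow a description of emails to all admitting clinicians in each service line. Section 5.6 resolves this in favour of the pilot clinicians, 52 by sections 3 and 3.2. Nothing invites excluded or opted-out clinicians to answer anything.

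**Who the aim is about.** The Aim 3 hypothesis in section 2.1 has as its subject specialists exposed to TUT Service + VM. Section 5.6 measures opinions and experience with the alerts used in the study. Both describe people who worked under the study conditions, and the surveyed group contains them. Clinicians who never entered could report only barriers they expect, which is a different question.

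**Who is counted.** Sections 5.7 and 7.2 cover enrolled or accrued subjects, so neither counts those who left beforehand. Section 7.2 does bear on the reverse case, an unwilling clinician who stays enrolled, because eligibility breaches are monitored. Opt-outs reach study staff through the contact given in the recruitment email. The plan does not require them to be tallied, but they can be.

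**How many are left out.** Let u be the share of approached clinicians who are unwilling and f the share of those who actually leave. The documents give neither, so both are assumed.

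- If nobody leaves (f = 0), the number unasked is 0 for every u. Passive recruitment, identification from the EMR and the lack of any described willingness check make a value near this plausible.
- If clinicians are approached until 52 remain, the number approached is N = 52/(1 − uf) and the number unasked is N·u·f. At f = 1: u = 5% gives N = 54.74 and 2.7 unasked; u = 20% gives N = 65 and 13 unasked. At f = 0.5 and u = 10%: N = 54.74, 2.7 are unasked and 2.7 remain, which is 2.7/52 = 5.3% of the sample.
- If instead a large part of the pool is emailed (section 3 gives several hundred; take 300 as an assumption), f = 1 gives 300 × 5% = 15 to 300 × 20% = 60 unasked.

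The range runs from 0 to 60, depending on u, f and the recruitment model. The documents do not settle it, and none of these counts is a finding about the trial.

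**What it does to the results.** The Aim 3 summary is a mean over respondents. For exposed clinicians, that mean is defined without those who never enrolled, so their absence does not bias it. The comparisons in Aims 1 and 2 do not use the survey.

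**The case for a change.** The best case for a change rests on purpose. Aim 3 is meant to guide dissemination, section 9.4 looks ahead to a larger trial under real-world conditions, and refusal to use VM is an obstacle such a trial would meet. A recruitment log costs little. The survey also already reaches control-arm clinicians, who have had no VM exposure either, so lack of exposure alone does not seem to disqualify a respondent.

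Part of this stands. The survey cannot describe outright refusers, and the plan should not be read as if it could. The missing count and the unstated way of applying section 3.4 are real omissions of detail. The rest is weaker. Control-arm clinicians are pilot participants who used a study alert, whereas those who never entered stand outside the study. Reluctance is not wholly lost, because enrolled clinicians may be hesitant without refusing, and perceived effectiveness, workflow and cognitive biases can still be measured among them. Inviting clinicians who declined would need further IRB approval, would probably reach a small group, and would add a separate set of anticipated barriers that could not properly be averaged with the ratings of exposed clinicians. That is an optional extension on which statisticians could reasonably differ.

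**Conclusion.** The observation is accurate: clinicians who leave before enrolment because they will not use VM are not surveyed, and no described step counts them. It does not call for a change. Followed as written, the plan gives a sound descriptive answer for clinicians who worked with the intervention, which is the Aim 3 hypothesis. The number left out is unknown and may be near zero, and no effect on any mean rating or on Aims 1 and 2 is shown.

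What remains is reporting that a competent analyst supplies without an amendment: the number excluded or opting out, with reasons where volunteered, and a statement that the Aim 3 conclusions apply to enrolled clinicians. This judgement rests on reading the survey sample through section 5.6 and the aim through its hypothesis in section 2.1. The survey form was not available, so its items are not judged here.

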3.6 Vulnerable Populations

Population protected under HHS regulations 45CFR46 Subparts B, C, & D Study Procedures: Children, neonates, and prisoners are not included in this research study. Women who are pregnant at the time of baseline assessments will be eligible for the study.

Populations vulnerable to undo influence or coercion: Educationally or economically disadvantaged persons are included but not solely targeted for recruitment. Cognitively impaired persons are not included in the current study. Because of our recruitment efforts for this study, it is possible that University of Pennsylvania employees and students may be invited to participate. Status of participation in the study will be independent of the subject's work or school activities.

4 Investigational Plan

4.1 General Design

To achieve all of our research objectives, we plan to conduct a two-arm RCT pilot study of a CDS intervention, exposing half of our clinician sample to the TUT Service+VM condition during clinical workflow and comparing important outcome measures to those observed among the half exposed to the current usual care condition, TUT Service alone. Following the conclusion of the pilot study, clinicians will be surveyed about implementation preferences and barriers influencing effectiveness of the intervention.

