6.1 Sample Size and Power Determination

Engagement rates are our primary measure of effect. Given that our initial educational intervention was able to change absolute engagement rates by approximately 20%, we assume that a CDS intervention would need to accomplish an equivalent amount of change to be clinically relevant. There are over 1000 BPA activations annually, resulting in approximately 600 TUT Service referrals per year (Engagement rate ~ 60%). To detect improvement in Engagement rate to 80%, with 80% power and a significance level of $p=0.05$, we need to enroll 24 clinicians to each arm. Retention: Because of project nature, we assume drop-out will be minimal (<10%) after enrollment; 26 subjects per arm ensures power.

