6.2 Statistical Methods

For Aims 1 and 2, rate comparisons between the two groups will be performed using Chi-square. We will examine the impact of the intervention on tobacco treatment rates across cancer inpatients, non-cancer in-patients, and all in-patients.

7 Safety and Adverse Events

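### The plan describes no balancing or adjustment for service line, although its 52 clinicians come from two lines and its Chi-square does not cover the resulting chance imbalance

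*Combined protocol and SAP*

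**What the plan says.** Section 4.1 presents a two-arm randomised pilot and describes allocation only as "exposing half of our clinician sample to the TUT Service+VM condition during clinical workflow". Section 3.2 fixes the number: "A total of 52 clinicians will be recruited to participate in the study from PPMC". Section 6.1 makes that 26 per arm.

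Recruitment in section 3.5 goes through leaders of "hospital-based service lines (Teaching Medicine and Hospitalist services) will be briefed on the purpose and procedures". Individual admitting clinicians in each line are then emailed, and enrolment is passive.

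Section 6.1 states "Engagement rates are our primary measure of effect" and sets the aim: "To detect improvement in Engagement rate to 80%, with 80% power", from a current rate of about 60%. In section 4.2 the ordering and referral rates have patients as their denominator, counted by arm, so clinicians with more alerts weigh more. Section 6.2 says that "rate comparisons between the two groups will be performed using Chi-square" and adds results for cancer, non-cancer and all inpatients.

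No section gives a randomisation method, a stratification factor, blocks or a balance check. No analysis includes service line. The documents report no line sizes, alert volumes or engagement rates by line.

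**The concern.** Service line is visible at recruitment and could plausibly go with different ordering habits. With only 26 clinicians per arm, one line can by chance be over-represented in one arm, and unequal alert volumes make this more likely. Part of the observed arm difference would then reflect the lines' usual rates. An analysis whose standard error reflected variation between clinicians would allow for this. A Chi-square on pooled patients treats patients as independent, so its p-value does not. At stake are some loss of precision and a false-positive rate above the nominal 5%, both depending on how far the lines differ.

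**Working it through.** **The plan's own figures.** The plan gives no figure for imbalance. The nearest is 24 clinicians per arm for 60% against 80%. The two-proportion formula gives [1.96√(2×0.7×0.3) + 0.842√(0.6×0.4 + 0.8×0.2)]² / 0.2² = (1.270 + 0.532)² / 0.04 ≈ 81.2, so 82 per arm, not 24. A comparison of clinician-level mean rates, n = 2(1.96 + 0.842)² SD² / 0.2², gives 24 with an SD of about 0.245 to 0.247, which the plan does not state. I use 0.245 only to illustrate the precision gain below.

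**Inputs from the documents.** 52 clinicians, 26 per arm (3.2, 6.1); two lines (3.5); rates of 60% and 80% (6.1); over 1,000 alerts a year (6.1); 18 months of data collection (3.1).

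**Assumptions.** 26 clinicians per line; a between-line gap g of 5, 10 or 20 points; alert volume per clinician either equal or gamma-distributed with CV 0.5 or 1.0.

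**Step 1: imbalance with equal volumes.** Let X be the number of clinicians from one line who fall in the intervention arm. X is hypergeometric with variance 26 × ½ × ½ × 26/51 = 3.31, so SD 1.82. The difference in line share between arms is D = (2X − 26)/26, with SD 2 × 1.82/26 = 0.140. The shift in the arm difference is D × g, so its SD is 0.7, 1.4 and 2.8 points for g = 5, 10 and 20. A 10/42 mix of lines lowers the SD of D to 0.110.

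**Step 2: unequal volumes and stratified allocation (40,000 simulated allocations).**

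| Gap (points) | SD of shift, CV 0 / 0.5 / 1.0 | Shift of 3 or more, CV 0 / 1.0 | Shift of 5 or more, CV 0 / 1.0 | SD after allocation 13/13 within line, CV 0 / 1.0 |
|---|---|---|---|---|
| 5 | 0.7 / 0.8 / 1.0 | 0% / 0.1% | 0% / 0% | 0 / 0.7 |
| 10 | 1.4 / 1.6 / 1.9 | 5% / 12% | under 0.1% / 0.8% | 0 / 1.4 |
| 20 | 2.8 / 3.1 / 3.9 | 40% / 45% | 5% / 20% | 0 / 2.7 |

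Stratified allocation removes the shift only when volumes are equal. With CV 1.0 about 70% of the SD remains (2.7 of 3.9), because clinician counts are balanced and patient counts are not.

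**Step 3: what the planned test does with it.** I simulated no intervention effect, line rates of 60% ± g/2, line as the only source of clinician variation, and 1,500 patients (1,000 × 1.5 years, assuming that alert volume applies to this sample). False-positive rates at a nominal 5% (20,000 trials per case):

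| Gap (points) | Plain Chi-square, CV 0 / 1.0 | Plain Chi-square after stratified allocation, CV 0 / 1.0 | Line-stratified (Mantel-Haenszel) test, CV 0 / 1.0 |
|---|---|---|---|
| 5 | 6% / 7% | 5% / 6% | 5% / 5% |
| 10 | 8% / 12% | 5% / 8% | 5% / 5% |
| 20 | 19% / 29% | 5% / 18% | 5% / 5% |

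With 500 patients the plain test gives 6% and 7% at a 10-point gap, and 10% and 14% at 20.

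**Step 4: gain in precision.** With a clinician SD of 0.245, the standard error of the arm difference is 0.245 × √(2/26) = 6.80 points. A 10-point gap contributes 0.10²/4 = 0.0025 of the variance of 0.0600, about 4%. Removing it gives √(0.0600 − 0.0025) × √(2/26) = 6.65 points. For a 20-point gap the standard error falls to 6.2 points.

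**The case against.** The strongest reply is that simple 1:1 randomisation of 52 clinicians is valid, that this is a pilot, and that chance imbalance is random error which a clinician-level standard error would cover. With such an analysis the gain from handling line is small: 6.80 to 6.65 points at a 10-point gap. This stands, and it is why the point is minor. It does not rescue the planned test, which has no clinician-level standard error.

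Second, nothing in the documents shows that the lines differ. The introduction reports variation between individual clinicians and says nothing about lines. A 20-point gap would equal the whole target effect. This also stands, so every size given here is conditional.

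Third, a reader might infer that the plan decided against stratification. It did not: it is silent on the randomisation method altogether, so the most that can be said is that none is described. A reader might also infer that the two lines join at different times because their leaders must first agree. Section 3.5 does not say so.

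Fourth, section 3.5 does not say that a clinician belongs to only one line. If some work on both, line is not a clean stratum without a rule. Finally, section 5.4 already speaks of clinicians as randomised, so allocation may be complete. In that case only the analysis change is available.

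**Conclusion.** The point holds as a low-cost improvement, not a serious flaw. As described, line is handled neither in allocation nor in analysis. With 26 clinicians per line, chance imbalance adds an SD of about 0.7 to 1.0 points to the arm difference for a 5-point gap, 1.4 to 1.9 for 10 and 2.8 to 3.9 for 20, against a 20-point target. The planned Chi-square ignores that error.

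The stronger reading, that imbalance will bias the trial by several points, is not supported. Imbalance under randomisation has no direction. Shifts of 3 points or more are negligible at a 5-point gap, occur in about 5% to 12% of allocations at 10 points, and become common only near 20. The results rest on the assumed line mix, gap and volume spread. The false-positive rates also rest on the assumed patient total and on line being the only clinician variation.

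**What to change.** - **Section 6.2, in either case:** replace the plain Chi-square with a comparison that includes service line, such as a line-stratified test or a regression with line as a factor. A covariate cannot simply be added to a Chi-square, so the test itself changes.
- **Section 4.1, only if allocation is not yet done:** state that clinicians are randomised 1:1 in blocks within service line, using the primary line for anyone who works on both. This alone is not enough, because about 2.7 points of SD remain at a 20-point gap with volume CV 1.0.

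The cost is a sentence in 4.1, a changed test in 6.2, a recorded line for each clinician and slightly more analysis work. No extra clinicians or patient data are needed. If the lines differ little, the gain is modest. Neither change replaces an analysis that accounts for clustering of patients within clinicians. That must be settled separately, and line can be one term in that model.
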